### 17.3 Clinical Laboratory Evaluation

All laboratory assessments are performed at local laboratories and comply with local requirements.

Laboratory values (including corresponding normal ranges) from local laboratories will be converted into the standard units by data management. The results in standard units will be used for the analyses.

Laboratory results will be classified according to the NCI-CTCAE toxicity grading version 4.03. If toxicities for high and low values of a specific parameter are defined, these toxicities will be analyzed separately for the parameter as “Parameter low” and “Parameter high”.

Laboratory results that are not part of the NCI-CTCAE will be presented according to the categories: below normal limits, within normal limits and above normal limits (according to the local laboratories normal ranges) by treatment arm.

The hematology differential parameters (Lymphocytes/Leukocytes (%), Neutrophils/Leukocytes (%), Monocytes/Leukocytes (%), Eosinophils/Leukocytes (%), Basophils/Leukocytes (%)) will only be listed.

The definitions for the NCI-CTCAE toxicity grading version 4.03 for each parameter are available in the [Appendix 3](#).

#### **NCI-CTCAE grades available:**

The worst on-trial grade, i.e. the highest CTCAE grade after the first dose of trial treatment will be summarized by parameter as follows:

- Number and percentage of subjects with grade  $\geq 0$ .
- Number and percentage of subjects with grade  $\geq 3$ .
- Number and percentage of subjects with grade = 4.

Tables will summarize, separately for hematology and biochemistry parameters, the shift from baseline grade to worst on-treatment grade by parameter and treatment group.

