6.4.1.2.2 Nonhematologic Toxicities

If a subject has a Grade 3 or 4 toxicity, as defined in Table 6.8, after 2 dose reductions, or if a treatment delay is longer than 3 consecutive weeks, then the discontinuation of chemotherapy treatment has to be considered.

Table 6.8 Criteria for Dose Reductions Based on Nonhematologic Toxicities on the Scheduled Day of Treatment

Toxicity	Grade ¹	Action to be taken
Mucositis	Grade 1	Delay chemotherapy treatment until Grade 0
	> Grade 1	Delay chemotherapy treatment until Grade 0; dose reduction of all further doses of 5-FU only by 20%
Diarrhea	Grade 1	Delay chemotherapy treatment until Grade 0
	> Grade 1	Delay chemotherapy treatment until Grade 0; dose reduction of all further doses of 5-FU only by 20%
Hypercreatinemia	≥ Grade 1	Delay chemotherapy treatment until Grade 0, change cisplatin to carboplatin
Ototoxicity	Grade 2	Dose reduction of all further doses of cisplatin by 20%
	> Grade 2	Delay chemotherapy treatment until ≤ Grade 2, change cisplatin to carboplatin
	> Grade 3	Stop carboplatin
Hand-foot syndrome	Grade 2	Delay chemotherapy treatment until ≤ Grade 1
	> Grade 2	Delay chemotherapy treatment until ≤ Grade 1; dose reduction of all further doses of 5-FU by 20%
Other organ toxicity ²	Grade 2	Delay chemotherapy treatment until Grade 1
	> Grade 2	Delay chemotherapy treatment until Grade 1 ³ ; dose reduction of all further doses of platinum-based treatment and 5-FU by 20% (or dose reduction of carboplatin to AUC 4 if applicable)
Sensory neuropathy	Grade 2	Dose reduction for all further doses of cisplatin by 20%
	> Grade 2	Stop cisplatin, change cisplatin to carboplatin
	> Grade 3	Stop carboplatin

5-FU: 5-fluorouracil.

The results of hematology and blood biochemistry analyses must be available before the start of each cycle of chemotherapy.

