8.5.4 Analysis of Safety

Safety analyses will be performed according to the as-treated principle. Any TEAEs will be summarized, i.e., those events that emerge during treatment having been absent pre-treatment, or worsen relative to the pre-treatment state and with onset dates occurring within the first dosing day of trial treatment until 30 days after the last dose of trial treatment. No formal statistical comparisons are planned.

The extent of exposure for cetuximab, cisplatin or carboplatin, and 5-FU will be characterized by duration (weeks), cumulative dose, dose intensity, relative dose intensity (actual dose given/planned dose), number of dose reductions, and number of dose delays.

AEs will be coded according to the current Medical Dictionary for Regulatory Affairs (MedDRA). The severity of AEs will be graded using CTCAE toxicity grades. The incidence and type of AEs, SAEs, trial treatment-related AEs and SAEs, trial treatment-related AEs by CTCAE toxicity grade, CTCAE Grade 3 and 4 AEs, trial treatment-related CTCAE Grade 3 and 4 AEs, AEs leading to death, AEs leading to discontinuation of trial treatment, will be summarized in total and for each treatment arm according to the MedDRA system organ class and MedDRA preferred terms. Missing classifications concerning trial treatment relationship will be considered as related to the trial treatment.

All deaths, deaths within 60 days after date of first dose of trial treatment and deaths within 30 days after last dose of trial treatment as well as reasons for deaths will be tabulated.

Laboratory results will be classified according to the CTCAE (version 4.03) when applicable. The worst on trial grade after date of first dose of trial treatment will be summarized. Shifts in toxicity grading from treatment start to highest grade will be displayed. Results for variables that were not part of the CTCAE (version 4.03) will be presented as below, within, and above the normal limits of the local laboratory. Only subjects with post-baseline laboratory values will be included in these analyses. The last measurement before trial treatment will serve as the baseline measurement.

Vital signs (temperature, heart rate, blood pressure, respiratory rate) will be descriptively presented.

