## 9 Changes to the Planned Analyses in the Clinical Trial Protocol

Not Applicable.

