### 17.2.3 Special Adverse Events Categories

Special safety summaries will be performed for special adverse event categories (SPAEC):

- Acne-like rash
- Skin reaction
- Infusion related reaction
- Neurotoxicity associated AEs
- Mucositis
- Septic events
- Cardiac events

The latest special AE list provided by drug safety will also be referred. If there are any difference, the special AE list provided by drug safety has higher priority.

The SPAEC “Infusion related reaction” is further divided into the following medical concepts:

- Allergy/anaphylaxis
- Dyspnea
- Fever
- Other

The SPAEC “Cardiac events” is further divided into the following medical concepts:

- Congestive Heart Failure
- Arrest
- Infarction-ischemia
- Arrhythmia
- Sudden death

The AEs are associated to a category by matching with a list of predefined PT.

The AEs are associated to a category by matching with a list of predefined PT. For the Infusion related reactions, there are 2 categories of events:

- AEs flagged in the definition as “Inclusion of AEs on Day 1 only” = No: any TEAE with the corresponding preferred term will be taken into account
- AEs flagged in the definition as “Inclusion of AEs on Day 1 only” = Yes: AEs with the corresponding preferred term occurred at Cycle 1 Day 1

A listing with all preferred terms for each category and medical concept will be provided.

The following summaries will be produced for all SPAEC:

- Number of subjects with SPAEC events, overall and by medical concept if applicable
- Number of subjects with SPAEC events by NCI-CTCAE grade (any, 1, 2, 3, 4, 5,  $\geq 3$ ), overall and by medical concept

Special summaries will be prepared separately for events on “skin reactions” and “acne-like rash” (=SPAEC1) only for the patients who received at least one dose of cetuximab as follows:

- Time until first occurrence of any “SPAEC1”
  - 1-7 days,
  - 8-14 days,
  - 15 -21 days,
  - 22-28 days,
  - 29-35 days,
  - 36-42 days,
  - $\geq 43$  days
- Time until first occurrence of grade 3/4 “SPAEC1” by category:
  - 1-7 days,
  - 8-14 days,
  - 15 -21 days,
  - 22-28 days,
  - 29-35 days,
  - 36-42 days,
  - $\geq 43$  days
- The resolution status of SPAEC1 after cetuximab discontinuation
  - 0 days (resolved during treatment),
  - resolution within days 1-30,
  - 31-60,
  - 61-90,

- 91-120,
- >120.
- The resolution status of SPAEC1 Grade 3/4 after cetuximab discontinuation
  - 0 days (resolved during treatment),
  - resolution within days 1-30,

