#### **NCI-CTCAE grades not available:**

The worst on-treatment value for hematology and biochemistry parameters which cannot be graded per NCI-CTCAE will be summarized by parameter according to the local laboratories normal ranges as follows:

- Lowest value after the first dose of trial treatment will be summarized according to Low category (value below normal limits) and Normal category (value within normal limits or above normal limits).
- Highest value after the first dose of trial treatment will be summarized according to Normal category (value within normal limits or below normal limits) and High category (value above normal limits).

Additional tables will summarize, separately for hematology and biochemistry parameters, the shift from baseline to worst on-treatment value by parameters and treatment group. The following categories of values will be used: Low/Normal/High/Missing.

Listings of all hematology and biochemistry values and also abnormal hematology and biochemistry values will also be provided. Abnormal values are defined as values outside of normal ranges. The following information will be included in those listings in addition to the subject ID and treatment arm:

- Selected dosing information: date of first / last administration separately for cetuximab, cisplatin, carboplatin, and 5-FU.
- Laboratory parameter with unit.
- Visit of laboratory parameter measurement
- Collection date of laboratory parameter
- Value of laboratory parameter
- Local laboratories normal ranges for laboratory parameter (lower limit of normal and upper limit of normal).
- Normal range indicator for value of the laboratory parameter (Low, Normal, High).
- Associated grade for value of the laboratory parameter according to NCI-CTCAE.

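### The lowest row of the worst laboratory grade table (SAP 17.3) is grade 0 or higher, which every subject with a graded value meets, so the table shows no any-grade rate

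*SAP*

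**What the plan says.** SAP section 17.3, under the subheading for parameters with CTCAE grades, takes the highest grade after the first dose for each parameter and lists three rows. The first is "Number and percentage of subjects with grade $\geq 0"; the others are grade 3 or higher and grade 4. The next sentence plans tables, separately for hematology and biochemistry, of "the shift from baseline grade to worst on-treatment grade by parameter and treatment group".

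Protocol section 8.5.4 sets the requirement: "The worst on trial grade after date of first dose of trial treatment will be summarized". It also sets the denominator: "Only subjects with post-baseline laboratory values will be included in these analyses". SAP section 9, headed "Changes to the Planned Analyses in the Clinical Trial Protocol", is marked as not applicable, so the SAP declares no departure from that.

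SAP Appendix 3 begins Grade 1 above the upper limit of normal for ALT and AST, and below the lower limit for low magnesium. Protocol Table 6.8 (section 6.4.1.2.2) uses Grade 0 for the level below Grade 1 of a laboratory finding. For hypercreatinemia of Grade 1 or more the action is "Delay chemotherapy treatment until Grade 0, change cisplatin to carboplatin".

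**The concern.** A row that every evaluable subject satisfies cannot vary with treatment. The natural first row of such a table is any abnormality, that is, grade 1 or higher, and here it is missing. Comparable SAP summaries have that level. For ungraded parameters the lowest value is split into "Low category (value below normal limits) and Normal category (value within normal limits or above normal limits"), with a matching split for the highest value. The special adverse event categories in section 17.2.3 are tabulated as "Number of subjects with SPAEC events by NCI-CTCAE grade (any, 1, 2, 3, 4, 5") with a further row for grade 3 or higher.

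At stake is the visibility of mild and moderate laboratory toxicity. Protocol Table 3.1 lists hypomagnesaemia and raised liver enzymes as very common with cetuximab. The adverse event tables cover these only in part. Under Protocol section 7.4.1.1, a Grade 1 to 3 laboratory finding becomes an adverse event only if it is symptomatic, leads to discontinuation or is judged medically important. Section 7.4.3 adds results that cause an interruption or dose reduction. Hypomagnesaemia is a Tier 1 event in SAP section 17.2.4, but only cases reported as adverse events are counted there. An asymptomatic Grade 1 or 2 change that needs no action can therefore be absent from every adverse event table.

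**Working it through.** No figure in the plan needs reproducing; the check is on what the three rows can show.

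**Notation.** For one parameter and one arm, let n be the subjects with a graded post-baseline value (Protocol 8.5.4), and n0, n12, n3 and n4 those whose worst grade is 0, 1–2, 3 and 4. Then n = n0 + n12 + n3 + n4.

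**Rows as planned.**
- Grade ≥0: (n0 + n12 + n3 + n4)/n = n/n = 100%, in each arm.
- Grade ≥3: (n3 + n4)/n.
- Grade 4: n4/n.

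From these a reader recovers n4, n3 and the sum n0 + n12: three groups, with Grade 0 pooled with Grades 1 and 2. The any-grade rate, (n12 + n3 + n4)/n, cannot be recovered. The between-arm difference in the first row is 100% − 100% = 0 points for any pair of true any-grade rates.

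**Rows with ≥1 in place of ≥0, plus n.** A reader recovers n0 = n − (n12 + n3 + n4), then n12, n3 and n4: four groups.

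**Illustration.** The planned 240 subjects at 2:1 give 240 × 2/3 = 160 and 240 × 1/3 = 80. The grade distributions are assumptions, not document figures: true any-grade rates of 70% in Arm A and 30% in Arm B. One simulated draw with no missing values gave:

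| Row | Arm A (160) | Arm B (80) |
|---|---|---|
| ≥0 | 100.0% | 100.0% |
| ≥1 (not planned) | 70.6% | 30.0% |
| ≥3 | 18.1% | 2.5% |
| 4 | 5.0% | 2.5% |

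The planned first row shows no difference; the missing row shows 70.6 − 30.0 = 40.6 points.

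**Other possible denominator.** SAP section 11 has a default, unless otherwise stated: the full analysis set, with missing observations counted. Under it the first row equals the share of subjects with a graded post-dose value. With assumed missingness of 3% and 5%, simulated draws gave 94.4% to 98.8%. That measures data availability, not toxicity.

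**The case against.** The strongest reply is that the shift tables in the next sentence already give the full worst-grade distribution by parameter and arm, and that the listings show the grade of each value. Protocol section 8.5.4 asks for the worst grade and for shifts but prescribes no cut-points. A short table focused on Grades 3 and 4, with detail in the shift table, is a legitimate layout. That stands to the extent that no data are lost, and it is why the point is minor. It does not give the first row any content.

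Second, exactly 100% depends on the Protocol denominator, which SAP 17.3 does not repeat. That is correct. Under the SAP default the figure can fall below 100%, but it still carries no any-grade information.

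Third, the row may be meant as the evaluable count. The SAP does not say so, and the table would still lack an any-grade row.

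Fourth, the sign could be a slip for a strict inequality. If grade above 0 is what the sponsor intends, correcting the sign settles the matter. The neighbouring grade 3 row has the same sign, so nothing shows that it was misprinted.

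Finally, a plain any-grade count mixes baseline abnormality with on-treatment change for ALT and AST. That is true, and it bears on how the new row should be read.

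**Conclusion.** The concern holds as a minor, descriptive defect. As written, the first row is 100% in both arms under the Protocol 8.5.4 denominator, and a measure of data availability under the SAP default. Under neither does the table give an any-grade rate, and it separates three grade groups where four are available. The conclusion rests on values inside the normal limits being Grade 0, which follows from Appendix 3 and from the Protocol's own use of the term. The effect is confined to this one safety table. Any-grade counts can be summed from the shift tables, no formal safety comparison is planned, and no efficacy result or decision rule changes.

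**What to change.** In SAP section 17.3, change the first row to grade 1 or higher, and print for each parameter and arm the number of subjects with a post-baseline value, stated as the denominator in line with Protocol section 8.5.4. If the existing row was meant as that number, label it n and add the grade 1 or higher row.

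Keep the shift tables for treatment-emergent change. Inclusion criterion 8 allows ALT and AST up to 3 × ULN at entry (5 × ULN with liver metastasis), which is already Grade 1 to 2, so the new row will include baseline abnormalities. Inclusion criterion 9 requires magnesium within the normal range, so for low magnesium the row should be closer to on-treatment incidence. It is not identical, because electrolyte correction is allowed during screening.

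The cost is one character in the SAP and one row in the table program, or one added row and a label. No additional data are needed.

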#### **NCI-CTCAE grades not available:**

The worst on-treatment value for hematology and biochemistry parameters which cannot be graded per NCI-CTCAE will be summarized by parameter according to the local laboratories normal ranges as follows:

- Lowest value after the first dose of trial treatment will be summarized according to Low category (value below normal limits) and Normal category (value within normal limits or above normal limits).
- Highest value after the first dose of trial treatment will be summarized according to Normal category (value within normal limits or below normal limits) and High category (value above normal limits).

Additional tables will summarize, separately for hematology and biochemistry parameters, the shift from baseline to worst on-treatment value by parameters and treatment group. The following categories of values will be used: Low/Normal/High/Missing.

Listings of all hematology and biochemistry values and also abnormal hematology and biochemistry values will also be provided. Abnormal values are defined as values outside of normal ranges. The following information will be included in those listings in addition to the subject ID and treatment arm:

- Selected dosing information: date of first / last administration separately for cetuximab, cisplatin, carboplatin, and 5-FU.
- Laboratory parameter with unit.
- Visit of laboratory parameter measurement
- Collection date of laboratory parameter
- Value of laboratory parameter
- Local laboratories normal ranges for laboratory parameter (lower limit of normal and upper limit of normal).
- Normal range indicator for value of the laboratory parameter (Low, Normal, High).
- Associated grade for value of the laboratory parameter according to NCI-CTCAE.

### **Urinalysis**

All urinalysis results as reported on the “Urinalysis” and “Urinalysis Microscopic Evaluation” eCRF pages will be listed.

### **Creatinine clearance**

Values for Urine creatinine, Serum creatinine and Creatinine clearance as reported on the “Creatinine Clearance” eCRF page will be listed.

### **Viral Serology**

All test results for Hepatitis B Virus (HBV) antigen, HBV antibody, Hepatitis C Virus (HCV) antibody, Human Immunodeficiency Virus (HIV) as collected on the “HBV, HCV, HIV Tests” eCRF page will be listed.

## 17.4 Vital Signs

Vital signs data will be summarized by treatment group for the Safety analysis set.

Body temperature, blood pressure (BP), heart rate, respiratory rate as well as the weight measurements, will be summarized in shift tables (including number of subjects and percentages) of baseline value versus worst on-treatment change from baseline will be provided for both increase and decrease.

Last assessments prior to first trial drug infusion will be taken into account to define the pre-treatment baseline value.

The following parameter categories will be used for shift tables:

| Parameter                      | Baseline categories                                    | Post-baseline categories                                   |
|--------------------------------|--|--|
| Systolic blood pressure (SBP)  | <140 / ≥140 mmHg                                       | Absolute change of:
=<20 / >20 - =<40 / >40 mmHg        |
| Diastolic blood pressure (DBP) | <90 / ≥90 mmHg   | Absolute change of:
≤ 20 / >20 - ≤40 / >40 mmHg         |
| Pulse rate                     | ≤100 / >100 bpm  | Absolute change of:
≤20 / >20 - ≤40 / >40 bpm           |
| Respiratory rate               | ≤20 / >20 bpm  | Absolute change of:
≤5/min, >5-≤10/min, >10/min         |
| Temperature                    | <37°C / 37°C - <38°C / 38 - <39°C / 39 - <40°C / ≥40°C | Absolute change of:
<1 / 1 - <2 / 2 - <3 / ≥3°C         |
| Weight                         | None (kg)  | Absolute change of:
<5% / ≥5 - <10% / ≥10 - <20% / ≥20% |

The missing and overall categories will also be shown in these tables.

All vital signs data (including body weight), as recorded in the “Vital signs” eCRF page, will be presented in a listing including the value at baseline and the change from baseline.

## 17.5 Other Safety or Tolerability Evaluations

### ECG

The “Result of ECG” parameter will be summarized by treatment arm for the Safety analysis set as follows: shift table from baseline to the worst on-treatment result will be tabulated with the subsequent categories:

- Normal ECG
- Abnormal ECG (includes clinically significant and not clinically significant)
- Missing
- Total

A listing of all ECG parameters results from the “Electrocardiogram” eCRF page will be provided.

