Combination with 5-FU: When cetuximab was used in combination with intermittent infusional 5-FU, the frequencies of cardiac ischemia including myocardial infarction and congestive heart failure as well as the frequency of hand-foot syndrome (palmar-plantar erythrodysesthesia) were increased compared to infusional 5-FU alone.

Combination with platinum-based chemotherapy: If cetuximab is used in combination with platinum-based chemotherapy, the frequency of severe leukopenia or severe neutropenia may be increased, and thus may lead to a higher rate of infectious complications such as febrile neutropenia, pneumonia, and sepsis compared to platinum-based chemotherapy alone.

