Renal function will be assessed on a regular basis as specified in the protocol (see Table 1.1). Cisplatin should be used with caution in subjects with pre-existing peripheral neuropathy. Cisplatin is contraindicated in subjects with a pre-existing hearing deficit. Audiometric testing and periodic neurological examination at baseline and during treatment are recommended to monitor the effects of cisplatin on hearing and neurological function.

Major toxicities observed with carboplatin: myelodepression with thrombopenia, leucopenia, neutropenia and/or anemia; infectious complications; nausea and vomiting; ototoxicity; and peripheral neuropathies.

Major toxicities observed with 5-FU:

- Cardiac toxicity: The typical signs of cardiac toxicity related to 5-FU are ischemic pain occurring a few hours after a bolus or after the start of a continuous infusion, together with characteristic ECG changes. Silent ECG alterations may also occur. Myocardial infarction has been reported. Thus, treatment with 5-FU must be stopped in subjects who develop such symptoms or have any other cardiac events of unclear origin during or after treatment with 5-FU.
- Hand-Foot syndrome: Subjects treated with 5-FU may develop hand-foot syndrome, characterized by redness and swelling of the palms and soles of the feet. Mild hand-foot syndrome is painless, but in 10 to 15% of cases it can be painful and is usually associated with blisters, ulcerations, cracks, and desquamation. Pyridoxine (vitamin B6) at 100-150 mg per day may be helpful.
- Diarrhea and mucositis: Subjects treated with 5-FU may develop mucositis, or more commonly diarrhea. In case of diarrhea, symptomatic treatment with loperamide is recommended.

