Investigators must also systematically assess the causal relationship of AEs to the IMP/trial treatment (including any other non-IMPs, radiation therapy, etc.) using the following definitions. Decisive factors for the assessment of causal relationship of an AE to the IMP/trial treatments include, but may not be limited to, temporal relationship between the AE and the IMP/trial treatments, known side effects of IMP/trial treatments, medical history, concomitant medication, course of the underlying disease, trial procedures.

Unrelated: Not reasonably related to the IMP/trial treatments. The AE could not medically

(pharmacologically/clinically) be attributed to the IMP/trial treatments under study in this clinical trial protocol. A reasonable alternative explanation must be available.

Related: Reasonably related to the IMP/trial treatments. The AE could medically

(pharmacologically/clinically) be attributed to the IMP/trial treatments under study

in this clinical trial protocol.

Abnormal Laboratory Findings and Other Abnormal Investigational Findings

Abnormal laboratory findings (Grade 1-3) and other abnormal investigational findings (for example, on an ECG trace) should not be reported as AEs unless they are associated with clinical signs and symptoms, lead to treatment discontinuation or are considered otherwise medically important by the Investigator. If a laboratory abnormality fulfills these criteria, the identified medical condition (for example, anemia, increased ALT) must be reported as the AE rather than the abnormal value itself.

For abnormal laboratory findings, which are recorded as AE, follow up measures should be performed.

Serious Adverse Event

An SAE is any untoward medical occurrence that at any dose:

- Results in death.
- Is life-threatening. (Note: The term "life-threatening" refers to an event in which the subject is at risk of death at the time of the event, not an event that hypothetically might have caused death if it was more severe.)
- Requires inpatient hospitalization or prolongs an existing hospitalization.
- Results in persistent or significant disability or incapacity.
- Is a congenital anomaly or birth defect.

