7.4.4.4 Electrocardiogram

Dead.

A computerized 12-lead ECG must be obtained at the time points outlined in Table 1.1 and as clinically indicated. An ECG should be performed after the subject has rested for 5 minutes. Each lead shall be recorded for at least 3 beats at a speed of 25 mm/second.

The following parameters will be recorded: rhythm, ventricular rate, PR interval, QRS duration, QT interval, and corrected QT interval.

At screening, the Investigator must assess the ECG for signs of cardiac disease that could exclude the subject from the trial. An assessment of normal or abnormal will be recorded and if the ECG is considered abnormal, the abnormality will be documented in the eCRF. The ECG results must be available at start of each cycle visit.

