### **ECG and Vital Signs**

The table summarizing ECG and vital signs at baseline will be produced based on ITT analysis set.

The ECG overall assessment as reported by the investigator on the “Electrocardiogram” eCRF page will be summarized at baseline as follows:

- Number and percentage of subjects with result of ECG reported as Normal.
- Number and percentage of subjects with Abnormal result of ECG.

For vital signs, systolic and diastolic blood pressure, heart rate, body temperature, respiratory rate, weight measurements and body surface area (BSA) at baseline will be summarized.

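### The on-treatment ECG shift table pools clinically significant and minor abnormalities, which hides some worsening and dilutes the comparison between arms

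*SAP*

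**What the plan says.** SAP 17.5 summarises the overall ECG result by arm in the safety set: "shift table from baseline to the worst on-treatment result will be tabulated with the subsequent categories". The categories are Normal, Abnormal, Missing and Total, and the second is defined as "Abnormal ECG (includes clinically significant and not clinically significant". The only other ECG output in that section is a listing ("A listing of all ECG parameters results from the" Electrocardiogram eCRF page). At baseline, SAP 13.3 uses the same two classes, with "Number and percentage of subjects with Abnormal result of ECG" as the abnormal line.

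Protocol 7.4.4.4 has each ECG record "rhythm, ventricular rate, PR interval, QRS duration, QT interval, and corrected QT interval". None of these is tabulated.

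Three protocol statements give the context:

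- Section 3.7.4 reports that, with cetuximab plus intermittent infusional 5-FU, "the frequencies of cardiac ischemia including myocardial infarction and congestive heart failure" were higher than with infusional 5-FU alone.
- Section 6.4.1.2, on 5-FU cardiac toxicity, warns: "Silent ECG alterations may also occur".
- Section 7.4.1.1 states that "other abnormal investigational findings (for example, on an ECG trace) should not be reported as AEs unless they are associated with clinical signs and symptoms", with two further exceptions: findings that lead to treatment discontinuation, and findings the Investigator considers medically important for another reason.

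**The concern.** A shift table is meant to show who got worse. With CS and NCS abnormalities in one class, one kind of worsening disappears: NCS at baseline followed by CS on treatment lands in the Abnormal-to-Abnormal cell. In subjects normal at baseline, a trivial finding and a significant one are counted alike, so the Normal-to-Abnormal cell cannot show how much of any difference between arms matters clinically.

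Safety is a secondary objective, the two arms differ by the addition of cetuximab to infusional 5-FU, and the protocol itself names a cardiac risk of that combination and silent ECG changes with 5-FU. Echocardiography is scheduled at screening only (Table 1.1), so the ECG is the scheduled cardiac investigation that is repeated during treatment. The SAP keeps severity levels elsewhere: laboratory shifts use CTCAE grades (17.3), vital signs use graded change classes (17.4), and ECOG shifts are by performance status (17.5).

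**Working it through.** **1. No figure to reproduce.** The plan states no ECG rate and no calculation on this point. The mechanism is checked from the category definitions, and the size is then illustrated with assumed rates.

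**2. Where each pattern lands.**

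| Baseline | Worst on treatment | Cell in the planned table |
|---|---|---|
| Normal | NCS | Normal to Abnormal |
| Normal | CS | Normal to Abnormal |
| NCS | NCS | Abnormal to Abnormal |
| NCS | CS | Abnormal to Abnormal |

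Rows 1 and 2 cannot be told apart, nor can rows 3 and 4. Row 4 is real worsening placed in the no-change cell.

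**3. What the AE tables add.** An ECG finding enters the TEAE tables (SAP 17.1) only through one of the three exceptions in Protocol 7.4.1.1. It enters the Cardiac events category (SAP 17.2.3) only if it is already an AE and its preferred term is on the predefined list. For a symptom-free change that does not lead to discontinuation, the one remaining route is the Investigator's judgement of medical importance. Protocol 8.5.4 says that clinically significant physical examination findings are to be reported as AEs; neither document says the same of ECGs.

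**4. Illustration.** From Protocol 5.1: about 240 subjects at 2:1, so 240 × 2/3 = 160 in Arm A and 240 × 1/3 = 80 in Arm B. Everything else is assumed:

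- share *b* with an NCS abnormality at baseline: 20%, 40% or 60%, the rest normal
- new CS change: *c*A = 10% in Arm A and *c*B = 4% in Arm B, independent of baseline
- new NCS change in baseline-normal subjects without a CS change: *m* = 20% in both arms.

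Formulas:

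- New CS changes hidden in Abnormal-to-Abnormal = *b* × *n* × *c*, so the hidden share of all new CS changes is *b*.
- Normal-to-Abnormal rate = (1 − *b*) × [*c* + (1 − *c*) × *m*].

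The bracket is 0.10 + 0.90 × 0.20 = 0.280 in Arm A and 0.04 + 0.96 × 0.20 = 0.232 in Arm B. New CS changes number 160 × 0.10 = 16 and 80 × 0.04 = 3.2.

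| *b* | Hidden, Arm A (of 16) | Hidden, Arm B (of 3.2) | Normal to Abnormal, A | Normal to Abnormal, B | Ratio |
|---|---|---|---|---|---|
| 20% | 3.2 | 0.6 | 22.4% | 18.6% | 1.21 |
| 40% | 6.4 | 1.3 | 16.8% | 13.9% | 1.21 |
| 60% | 9.6 | 1.9 | 11.2% | 9.3% | 1.21 |

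The true CS ratio is 10/4 = 2.5.

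**5. What drives each effect.** The hidden share depends only on *b*. The ratio shown does not depend on *b*, which cancels; it is [*c*A + (1 − *c*A)*m*] / [*c*B + (1 − *c*B)*m*]. With no trivial findings (*m* = 0) it is 2.5, at *m* = 20% it is 0.280/0.232 = 1.21, and as *m* approaches 100% it approaches 1. This assumes the same *m* in both arms. Cetuximab can continue beyond six cycles in Arm A, so a longer on-treatment window there could raise *m* in that arm.

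**The case against.** The case on the other side limits the point considerably.

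- *Other tables cover cardiac harm.* A reader might infer that this is the only summary able to capture silent cardiac harm, or that the plan cannot show such harm at all. The documents do not support that. Ischaemia, infarction and heart failure are clinical events reported as AEs, and SAP 17.2.3 tabulates Cardiac events by CTCAE grade and by concept, including infarction-ischaemia and arrhythmia. A silent ECG change judged medically important also becomes an AE. This stands, as partial cover.
- *The table is not uninformative.* It still shows new abnormality in subjects normal at baseline, and all ECG results are listed for case review. In the illustration the difference between arms is diluted, not lost. This stands.
- *The field is not confirmed.* Protocol 7.4.4.4, on screening, mentions only normal or abnormal plus a description, and SAP 13.3 uses the same two classes. The SAP 17.5 wording implies that CS status is recorded, but the eCRF is not among the documents. This stands.
- *CS status is itself an Investigator judgement.* The trial is open-label and neither document gives criteria, so the split table shares the weakness of the AE route. This stands. Unlike AE reporting, though, the assessment would be tabulated for every ECG taken.
- *No size can be claimed.* It is tempting to compound a per-ECG chance of a trivial finding over a fixed number of visits. Repeated ECGs in one person are not independent and the number on treatment varies, so such a figure would not be reliable. Nor does the plan compare safety formally (Protocol 8.5.4).
- *No commitment is breached.* The safety endpoints in Protocol 8.3.3 do not list ECG, and Protocol 8.5.4 specifies no ECG summary. This stands, and it is why the point is an improvement to a table rather than a failure to deliver one.

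**Conclusion.** The point holds as a minor safety-reporting improvement. That NCS-to-CS worsening is tabulated as no shift, and that new CS and trivial changes are mixed in baseline-normal subjects, follows from the category definitions and needs no assumption. How much is lost cannot be derived from the documents. Under independence from baseline, the hidden share of new CS changes equals the share of subjects with an NCS baseline abnormality. The fall in the ratio from 2.5 to 1.21 rests on the assumed CS and NCS rates and is illustrative only. No efficacy result, decision rule or sample size is affected.

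**What to change.** First confirm that the Electrocardiogram eCRF page records CS or NCS for each abnormal ECG. If it does, change SAP 17.5 as follows:

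- Use the shift categories Normal / Abnormal NCS / Abnormal CS / Missing / Total at baseline and on treatment, with the worst result taken in the order Normal, Abnormal NCS, Abnormal CS.
- Add one line per arm: number and percentage of subjects with a new on-treatment CS abnormality, with subjects without a CS abnormality at baseline as the denominator.

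The cost is SAP wording plus one extra row and column in an existing table, with no new data collection if the field exists. The drawback is that CS status is an open-label Investigator judgement, which a table footnote should state. If the field does not exist, the split cannot be made from that page as it stands, and the wording of the Abnormal category in SAP 17.5 should be corrected.
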